## ***D. Study Design***

The proposed study is a single-blinded randomized controlled trial. Participants will be recruited from patients at [name] neurosurgery practice, Neurosurgery Associates, L.L.C. (Columbus, OH) or at Neurological Associates, Inc at Riverside Methodist Hospital with [name]. Patients presenting with symptomatic, lumbar degenerative disc disease, and that meet the inclusion/exclusion criteria will be given information about the study and asked if they would like to participate.

Participants will be allocated to treatment groups using a block randomization scheme to increase the likelihood of balance. Treatment assignments will be stored in sealed, numbered envelopes that will be opened by study personnel in

the pre-operative period. The patient will be blinded to treatment assignment throughout the course of the study.

Participants will receive either standard DBM or experimental NuCel®, and will be blinded to which intervention they receive. All operations will be performed by [name] or [name]. Instrumentation will consist of titanium pedicle screws and rods. All operations will be done according to standard methods under fluoroscopic guidance and with electrophysiological monitoring.

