## II. METHODS

### *A. Study Population*

Participants will consist of patients presenting with symptomatic, one or two-level lumbar degenerative disc disease, spondylosis or spondylolisthesis. They must have failed traditional conservative treatment measures, such as pain medication, physical therapy, lumbar epidural steroid injections or lumbar bracing support, prior to surgery. They must be candidates for a one or two-level posterolateral lumbar fusion, with instrumentation, with or without laminectomy. The participants are patients that the surgeon would consider as low risk for non-union, and would have received only demineralized bone matrix (DBM) bone graft material without any other graft material, in particular, no recombinant human bone morphogenetic protein (rhBMP-2). Patients who would be considered higher risk of non-union, and who would have typically received rhBMP-2 will be excluded according to the list below.

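### No stratification by surgeon or practice is described and the mixed models have no surgeon term, so chance imbalance in surgeon mix would go uncorrected

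*Combined protocol and SAP*

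**What the plan says.** All of this is in the combined protocol and SAP.

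- **Allocation (II.D, Study Design).** "Participants will be allocated to treatment groups using a block randomization scheme to increase the likelihood of balance". The section does not give the block size, say whether it is fixed or varied, name a stratification factor, or say whether there is one list or one per practice.
- **Concealment (II.D).** "Treatment assignments will be stored in sealed, numbered envelopes that will be opened by study personnel in" the pre-operative period.
- **Sites and surgeons (II.D).** Recruitment is from one neurosurgery practice "or at Neurological Associates, Inc at Riverside Methodist Hospital with [name"]. "All operations will be performed by" one of two named surgeons.
- **Blinding (II.D).** "The proposed study is a single-blinded randomized controlled trial". The patient is blinded and, under Radiological outcomes in II.C, so is the radiologist. No blinding of surgeons is described.
- **Eligibility (II.A, Study Population).** The population is described as "patients that the surgeon would consider as low risk for non-union".
- **Analysis (II.E, Statistical Analysis).** The ODI model has treatment group and time as its independent variables, and the same model serves for pain. A baseline characteristic is brought into the analyses only if it differs significantly between the groups.
- **Data recorded (II.C, Study Variables).** The demographic items named are gender, age, diagnosis and spinal level. Surgeon and practice are not among them.

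**The concern.** Blocking on a single list balances the totals in the two arms. It does not balance the arms within each surgeon's patients. If the two surgeons' patients differ in ODI or pain, whether through case mix or technique, an uneven split of surgeons between arms moves the estimated treatment difference.

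The plan has three places where this could be handled: the allocation, the model and the baseline check. As written, the first two do not mention surgeon. The third would act only on a characteristic that is recorded and reaches significance. At stake is some precision in the primary contrast and a result that is harder to defend if the surgeon mix turns out visibly uneven.

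**Working it through.** **Inputs from the documents.** Planned enrolment is 60, 30 per arm (II.B). Baseline ODI is 52 with SD 8, and the hypothesised difference is 10% (II.B). There are two surgeons and two practices (II.D).

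**Assumptions not in the documents.** One shared list; fixed blocks of 4; each surgeon enrolling half the patients at random; a constant ODI difference between the two surgeons' patients of 2.6 to 8 points.

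**1. Target difference.** 10% × 52 = 5.2 ODI points. The stated sample size of 42 is not in dispute here.

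**2. Size of the chance imbalance.** With 30 patients per arm and surgeon unrelated to allocation, the SD of the difference in surgeon share is √(0.5 × 0.5 × 2/30) = 0.129, or 13 percentage points. A gap of 20 points means 18 versus 12 of 30, a difference of at least 6 patients. The difference between two independent Binomial(30, 0.5) counts is distributed as a Binomial(60, 0.5) count minus 30. The chance is therefore 2 × P(X ≥ 36) = 0.155. Simulation gives the same picture:

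| Surgeon split | Block size | One list: P(gap ≥ 20 points) | Stratified by surgeon |
|---|---|---|---|
| 50/50 | 4 | 0.152 | about 0 |
| 50/50 | 6 | 0.149 | about 0 |
| 70/30 | 4 | 0.115 | about 0 |
| 70/30 | 6 | 0.116 | about 0 |

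**3. Effect on the ODI contrast.** In a model without a surgeon term, shift = gap × surgeon effect. For a gap of 0.20:

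- effect 2.6: 0.2 × 2.6 = 0.52 points, 10% of 5.2
- effect 5.2: 0.2 × 5.2 = 1.04 points, 20%
- effect 8: 0.2 × 8 = 1.6 points, 31%

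**4. Would the baseline rule catch it?** For 18/30 versus 12/30, Fisher's exact p = 0.20 and the uncorrected chi-square p = 0.12. Neither is below 0.05, so no adjustment would follow even if surgeon were tested.

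**5. What stratifying the list would do to guessing.** Take a surgeon who sees only his or her own patients' assignments and always guesses the arm that is behind. Simulated accuracy with equal surgeon shares:

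| List | Fixed blocks of 4 | Random blocks of 2, 4 or 6 |
|---|---|---|
| One shared list | 54% | 54% |
| Separate list per surgeon | 70% | 70% |

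Varying the block size does not remove this advantage.

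**The case against.** **Chance imbalance is not bias.** Under randomisation the expected shift is zero, and the standard error and 5% error rate already allow for it. This stands. The typical effect is also smaller than the tail figures: a one-SD gap gives 0.13 × 4 = 0.5 to 0.13 × 8 = 1.0 points for effects of 4 to 8. The standard error of the treatment difference is 8 × √[(2/21) × (1 + 5ρ)/6], which is 1.2 to 2.3 for an assumed within-patient correlation ρ of 0.1 to 0.8.

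**The surgeon effect is assumed.** This stands too. An 8-point difference between two equal groups would account for (8/2)² / 8² = 25% of the ODI variance, which is large; 4 points would account for 6%.

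**The list may already be separate by practice.** The documents do not say. If so, the imbalance is near zero, but surgeon/practice is then a randomisation stratum and belongs in the model for that reason.

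**A stronger reading is tempting.** A reader might infer that the surgeons can predict allocations and select patients accordingly, since they place the graft, appear to be unblinded, and judge non-union risk. The documents do not establish this. They give no block size, do not say that blocks are fixed, and do provide sealed, numbered envelopes. With fixed blocks of known size, the share of allocations certain to someone who has seen every earlier one is 50%, 33% or 25% for blocks of 2, 4 or 6. Nothing says that either surgeon sees the other's assignments. On one shared list in blocks of 4, a surgeon seeing only his or her own half is certain about 1 time in 12 (8%), even with block position known. The 33% figure and the 15% imbalance figure therefore should not be added together: a surgeon reaches 33% from his or her own cases alone only with a separate list, where the imbalance largely disappears.

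**Conclusion.** The point holds as a modest, cheaply corrected weakness in the analysis. No stratification by surgeon or practice is described, neither mixed model has a surgeon term, surgeon is not named for recording, and the baseline rule would miss an 18 versus 12 split.

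If one shared list is used, a gap of 20 points or more in surgeon mix arises in about 11 to 15% of trials for surgeon splits of 70/30 to 50/50. It moves the ODI contrast by 0.5 to 1.6 points for an assumed surgeon effect of 2.6 to 8, against the 5.2-point target. The list structure, block sizes, surgeon shares and surgeon effect are all assumptions.

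Predictable allocation is possible but not shown. The silence on block size, envelope opacity and custody of the list is missing detail, not evidence of selection bias. Nor does it follow that the list must be stratified by surgeon: that removes the imbalance but raises a surgeon's guessing accuracy from about 54% to about 70%.

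**What to change.** In II.C, add surgeon and practice to the data recorded for every patient. In II.E, include surgeon/practice as a pre-specified fixed effect in the ODI and pain mixed models, whatever the baseline comparison shows. If the surgeon effect is additive, this removes the shift caused by uneven surgeon mix. The same term is right if the envelopes are kept as a separate series per practice.

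The cost is one model degree of freedom and one extra data item, with no added patients or visits, provided each surgeon corresponds to one practice, as II.D appears to describe.

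Stratifying the list by surgeon is optional. If the sponsor chooses it, the protocol should acknowledge that it makes allocation easier for an unblinded surgeon to guess, even with randomly varied blocks.

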### *Allografts*

**DBM** bone graft substitute (DBX; DePuy Synthes, West Chester, PA, USA) will be obtained via the Musculoskeletal Transplant Foundation (MTF), according to standard protocol. DBX putty consists of 93% demineralized bone content in a sodium hyaluronate carrier.

**NuCel®**, a stem-cell allograft, will be obtained from NuTech Medical, Birmingham, AL, USA. The bioactive amniotic suspension is derived from amniotic fluid and morselized amnion. Donors are pre-screened through questionnaires and laboratory tests. Amniotic tissue is collected at the time of scheduled Cesarian-section, and processed by NuTech under aseptic conditions. The product is approved by the Food and Drug Administration. The frozen contents of the NuCel® vial will be gently thawed, mixed with sterile saline, or the patient's blood, and then mixed with a cancellous bone chip carrier material.

Data will be collected by a member of the study team. Clinical outcome data will be collected in the office through the use of questionnaires (time points described above). Radiological data will be obtained from imaging location (time points described above).

A member of the study team will be responsible for the handling and storage of data. The identity of the participants will be kept confidential at all times. Participants will be given a number identifier for data entry and statistical purposes. Documents containing the identity of the patient will be restricted to those investigators authorized to work on the study. Further, these documents will be kept in a locked cabinet or safe, and stored with the study coordinator or other member of the study team.

### *Sources of Bias*

Efforts were made in designing this study to minimize the chance of study biases. We attempted to minimize the effect of additional medical conditions by having strict exclusion criteria. For example, patients who have any condition, such as diabetes, osteoporosis, or are smokers, are excluded from the study as these factors may have an effect on bone healing. All efforts are made to recruit groups that are as homogenous as reasonably possible. Participant bias will be

mitigated by blinding participants to the intervention they will receive. For clinical outcome measures, evaluator bias is minimized as the data will be collected through objective questionnaires to be filled out by the participants (pain scales, ODI). There is no need for evaluator judgment, which may be subjective, in recording these data. For radiological outcome measures, an independent, blinded radiologist will score the scans, eliminating evaluator bias. The only test that may be subject to evaluator bias is the neurological exam for sensory and motor deficits. Having said that, the neurological exam will be performed by [name], [name], a physician assistant (PA) or a nurse practitioner (NP) who is highly skilled and experienced in evaluating this test.

Since the only experimental intervention is at the time of surgery this study does not depend on patient adherence for the study intervention. The study will, however, depend on patients adhering to follow-up office visits and scans. We expect the “drop-out” rate will be low as most of these visits are required as follow-up to any surgery. Also, the final time point for data collection is 12 months after surgery, therefore, it is unlikely that the patient will seek surgical treatment elsewhere during this time frame.

#### ***E. Statistical Analysis***

We will first compare the demographic and pre-operative clinical characteristics of the NuCel® and DBM groups to evaluate randomization fidelity. If any characteristics are found to be statistically significant between the groups, this will be accounted for in the analyses of the primary and secondary outcomes. We will describe all categorical variables as percentages and continuous variables with means and standard deviations.

To evaluate our primary outcome we will use a linear mixed model with ODI score as the dependent variable and treatment group and time as independent variables. Mixed models are often preferred over a two-way ANOVA because they allow for incomplete data from participants and do not require a strictly normal distribution in the dependent variable. This model will also be used to evaluate the effect of treatment group on pain scores over time. Statistical significance will be set at  $p < .05$ .

We will report the frequency of observed fusion at the 6-month and 12-month follow-up periods via CT scan by treatment group. If our sample size allows, we will compare the NuCel® and DBM groups on fusion rates at each time point using Fisher’s Exact tests. Statistical significance will be set at  $p < .05$ .

We will report the frequency of adverse events experienced by the NuCel® and DBM groups including negative changes in neurological exam (sensory and motor) findings during the follow-up period.

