### ***B. Hypothesis***

We hypothesize that the NuCel® group will report, on average, Oswestry Disability Index (ODI) scores 10% lower than those of the DBM group. Assuming a baseline ODI score of 52 (SD=8) for the DBM group, 90% power and an a Type 1 error rate of 5%, a sample size of 42 patients (21 per group) would be sufficient to detect a 10% difference between groups using a repeated measures design with 6 measurement points. To account for drop-out, loss to follow-up, and/or refusal to complete study documents at follow-up, we plan to recruit a total of 60 patients (30 per treatment arm).

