### ***C. Study Variables***

#### Clinical outcomes

The following data will be collected at the time of enrollment (pre-operatively), and at 1, 2, 3, 6 and 12 months after surgery: 0-10 numeric pain rating scale for low back and leg pain, Oswestry Disability Index (ODI), and a neurological exam (sensory and motor evaluation). We will also record any adverse events (infection, inflammation, radiculopathy, etc.) that occur intra-operatively through 12 months. Demographic information including gender, age, diagnosis, spinal level for surgery, will be recorded directly into an Excel spreadsheet for each patient.

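### Pre-operative ODI and pain have no fixed place in the mixed models, and adjustment waits on a baseline significance test; always adjusting for the pre-operative value is a free gain, from nil to large.

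*Combined protocol and SAP*

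**What the plan says.** Section II.E first compares demographic and pre-operative clinical characteristics between the arms, then sets the covariate rule: "If any characteristics are found to be statistically significant between the groups, this will be accounted for in the analyses". The primary analysis is a "linear mixed model with ODI score as the dependent variable and treatment group and time as independent variables". For pain, "This model will also be used to evaluate the effect of treatment group on pain scores over time". No other covariate is named, no group-by-time term is stated, and the section does not say how a triggered characteristic would enter the model.

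ODI and pain are collected "at the time of enrollment (pre-operatively), and at 1, 2, 3, 6 and 12 months after surgery", which is one pre-operative and five post-operative assessments. Section II.B starts from "Assuming a baseline ODI score of 52 (SD=8) for the DBM group" and says that 21 per group, with 90% power, "would be sufficient to detect a 10% difference between groups using a repeated measures design with 6 measurement points". Six is reached only by counting the pre-operative visit. Section II.E does not say whether that visit is part of the outcome.

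**The concern.** In a randomised trial a baseline p-value measures chance imbalance. It does not show which characteristics predict the outcome, and that is what makes a covariate worth including. If randomisation is sound, pre-operative ODI will reach significance in about 5% of trials however strongly it predicts later ODI.

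The place of pre-operative ODI is also open, and there are two readings:

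- **(a)** The outcome is the five post-operative visits. Pre-operative ODI then enters only if its baseline test is positive, so about 95% of trials leave it out.
- **(b)** Pre-operative ODI is one of six responses. It is then always in the model, but how well it is used depends on a contrast that the plan does not name.

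At stake is power in a 60-patient trial, from a measurement that the schedule already requires.

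**Working it through.** **Inputs from the documents (Section II.B).** Mean 52 and SD 8 (given only for the DBM group at baseline); effect 10% of 52 = 5.2 points; type I error 5%; power 90%; 21 per arm needed, 30 per arm recruited.

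**Assumptions.** Two-sided test; SD 8 at every visit; the same 5.2-point effect at each post-operative visit; complete data; estimate averaged over the five post-operative visits. The documents give no correlations, so they are varied. Pairs are written (post-post, pre-post).

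**1. The plan's own figure.** For the mean of m equally correlated measurements, n per arm = 2V(1.960 + 1.282)²/5.2², with V = 64(1 + (m − 1)r)/m and (1.960 + 1.282)² ≈ 10.507. Setting n = 21 gives V = 21 × 27.04/(2 × 10.507) = 27.02. Solving for r gives 0.307 with m = 6 and 0.278 with m = 5. The stated 21 per group is therefore reproduced with a common correlation of about 0.3.

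**2. Patients per arm for 90% power.** Without adjustment, V = 64(1 + 4·r_post)/5. With adjustment, V = 64[(1 + 4·r_post)/5 − r_pre²].

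- (0.3, 0.3): V = 28.16 against 22.40, so 21.9 against 17.4
- (0.5, 0.3): V = 38.40 against 32.64, so 29.8 against 25.4
- (0.7, 0.3): V = 48.64 against 42.88, so 37.8 against 33.3
- (0.7, 0.7): V = 48.64 against 17.28, so 37.8 against 13.4

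**3. Reading (a): the plan's rule against always adjusting.** Simulation of pre-operative ODI (X) and the post-operative mean (M). The rule is a t-test on M, replaced by analysis of covariance on X when the baseline t-test on X has p < 0.05. Only ODI is used as a trigger. Power for ODI, rule vs always adjusting:

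| (post-post, pre-post) | 21 per arm | 30 per arm |
|---|---|---|
| (0.3, 0.1) | 86.9 vs 87.0% | 96.3 vs 96.2% |
| (0.5, 0.2) | 76 vs 78% | 89 vs 91% |
| (0.7, 0.2) | 65 vs 67% | 81 vs 83% |
| (0.3, 0.3) | 88 vs 93% | 97 vs 99% |
| (0.5, 0.3) | 76 vs 81% | 90 vs 93% |
| (0.7, 0.3) | 66 vs 70% | 81 vs 85% |
| (0.5, 0.5) | 77 vs 93% | 90 vs 99% |
| (0.7, 0.5) | 67 vs 81% | 82 vs 93% |
| (0.7, 0.7) | 68 vs 97% | 83 vs 99.7% |

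At pre-post correlation 0.1 and 21 per arm, the other two post-post values also show no gain: 75.3 vs 75.0% at (0.5, 0.1) and 65.5 vs 65.1% at (0.7, 0.1). At pre-post correlation 0, adjusting costs under 1 point (75.0 vs 74.2% at (0.5, 0), 21 per arm).

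**4. Reading (b): pre-operative ODI as a sixth response.** A group effect averaged over six visits is a test on (X + 5M)/6, which dilutes the effect to 5.2 × 5/6 = 4.33 points. A change contrast is a test on M − X. At 21 per arm, over the eight pairs in the table with pre-post correlation 0.2 or more, power is 51-76% for the six-visit average, 42-93% for change from baseline and 67-97% for adjustment. Both contrasts fall below adjustment in every pair. The closest case is (0.7, 0.7) at 30 per arm, where change gives 98.5% and adjustment 99.7%. A six-visit model with pre-operative means constrained equal matches adjustment: 93.3, 70.6 and 97.5% against 92.9, 69.8 and 97.3% at (0.3, 0.3), (0.7, 0.3) and (0.7, 0.7), 21 per arm. The plan does not describe such a model.

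**5. Type I error under reading (a), 30 per arm.** At (0.3, 0.3), (0.7, 0.3) and (0.7, 0.7), the rule gives 4.5, 4.7 and 3.1% overall. In the 32% of trials whose baseline gap exceeds one standard error it is 6.6, 6.0 and 8.3%; in the rest it is 3.4, 4.1 and 0.7%. Always adjusting gives 4.9-5.1% overall.

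**The case against.** **Baseline may already be in the model.** A reader might infer that pre-operative ODI enters only after a positive baseline test. The documents do not support that as fact: the six measurements of Section II.B make baseline-as-response at least as plausible. This objection stands, and the point is therefore that the role is not fixed. It does not rescue the plan, because neither natural six-visit contrast matches adjustment. The losses in step 4 do come from an undefined contrast and not from the significance-test rule, so they should not be read as the size of the rule's harm.

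**The gain rests on unknown correlations.** This also stands. The gain is already nil at pre-post correlation 0.1. At 0.3 throughout, with the planned 30 per arm, it is about 2 points (97 to 99%). The trial falls to 21 per arm only if 9 of 30 are lost (30%), and the Sources of Bias section expects few drop-outs.

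**The rule is pre-specified, uses baseline data only and is conservative overall.** Correct. A reader might infer from the 6-8% conditional figures that the rule inflates type I error. It does not: those figures select the trials with larger chance gaps, and the others fall below 5%.

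**Pain was not computed.** Correct. The documents give no SD or effect for pain. The variance argument carries over; the figures do not.

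**Conclusion.** The point holds as a free improvement in efficiency. Section II.E ties adjustment to a test that says nothing about prognostic value, and the plan leaves the place of pre-operative ODI unspecified.

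The size depends on the pre-post correlation. Against the plan's rule under reading (a), across 21-30 per arm, always adjusting costs under 1 point at 0, gains nothing at 0.1, gains about 1-5 points at 0.2-0.3 and about 8-29 points at 0.5-0.7. This rests on SD 8 at all visits, a constant 5.2-point effect, complete data and the average over five post-operative visits.

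Two stronger conclusions are not supported. The analysis is not invalid, since overall type I error is about 3-5%. Nor does adjustment secure 90% power at 21 per arm: at (0.7, 0.3) it reaches only 70%.

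**What to change.** In Section II.E, replace the conditional sentence with wording such as:

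*Whatever the baseline comparison shows, the ODI and pain mixed models use the five post-operative visits as the outcome and include the pre-operative value of that outcome as a fixed covariate; baseline significance tests do not determine adjustment.*

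An equivalent choice is all six visits as responses, with pre-operative means constrained equal between groups and the post-operative group difference tested. Write in one form only.

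In Section II.B, describe the same model, state the assumed pre-post and post-post correlations, and restate the power or per-group number they imply. For 90% power this is about 17.4 per arm at (0.3, 0.3) or 25.4 at (0.5, 0.3). Rewording the six measurements without redoing the calculation would leave the 21 per group unsupported. No increase in enrolment is required by this point.

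The cost is one sentence in Section II.E, a restated calculation in Section II.B and one model degree of freedom. Both pre-operative values are already collected. Dropping the baseline tests from the descriptive table, or changing the fusion comparison, is not needed.

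### The primary ODI model appears to count the pre-operative score as an outcome and has no prespecified baseline adjustment, so a 5.2-point benefit would be estimated as about 4.33

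*Combined protocol and SAP*

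**What the plan says.** - **Primary model (II.E):** "we will use a linear mixed model with ODI score as the dependent variable and treatment group and time as independent variables". The section states no treatment-by-time interaction, baseline term, covariance structure or primary contrast.
- **Sample size (II.B):** the hypothesis is that the NuCel arm "will report, on average, Oswestry Disability Index (ODI) scores 10% lower than those of the DBM group". The calculation starts from "Assuming a baseline ODI score of 52 (SD=8) for the DBM group" and arrives at 21 per group for 90% power "using a repeated measures design with 6 measurement points". Recruitment is set at 30 per arm to cover drop-out. No within-patient correlation is given.
- **Schedule (II.C, Clinical outcomes):** ODI is recorded "at the time of enrollment (pre-operatively), and at 1, 2, 3, 6 and 12 months after surgery", which is one pre-operative and five post-operative scores.
- **Baseline adjustment (II.E):** "If any characteristics are found to be statistically significant between the groups, this will be accounted for in the analyses".
- **Incomplete data (II.E):** mixed models are preferred partly because "they allow for incomplete data from participants".
- **Pain (II.E):** "This model will also be used to evaluate the effect of treatment group on pain scores over time".

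**The concern.** The intervention takes place at surgery (II.D, Sources of Bias), so the true treatment difference in the pre-operative ODI is zero. A main effect of group fitted to all six scores averages that zero with the five differences that can carry a benefit. The estimate shrinks towards zero and power falls.

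The pre-operative score is most useful as a covariate, where it reduces variance. The plan uses it that way only when a significance test between the arms happens to be positive, which under valid randomisation occurs in about 5% of trials. The plan therefore fixes neither how baseline ODI enters the primary analysis nor which contrast is the primary test.

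**Working it through.** **Inputs from the documents.** Difference 10% × 52 = 5.2 points; SD 8; 90% power; type I error 5% (taken as two-sided); 21 or 30 per arm; six ODI times, one pre-operative.

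**Assumptions.** Within-patient correlation ρ (not given, so a range is shown); equal correlation between all visits unless stated; a constant post-operative benefit; complete data unless stated.

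**1. The plan's own figure.** A single measurement needs 2 × [8 × (1.960 + 1.282) / 5.2]² = 49.7, so 50 per arm. Averaging m scores multiplies this by (1 + (m − 1)ρ)/m. For m = 6 the result is 49.7 × 0.400 = 19.9 at ρ = 0.28 and 49.7 × 0.417 = 20.7 at ρ = 0.30. With the noncentral t, 21 per arm has 90% power at ρ = 0.28. So 42 patients is consistent with a six-point main effect that carries the full 5.2 points at every point, including before surgery. It is not shown to be miscalculated.

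**2. What the literal model estimates.** With equal correlation each score has weight 1/6, so the expected group coefficient is (0 + 5 × 5.2)/6 = 4.33 for any ρ, with time categorical or linear. If correlation instead decays with actual months (0.5 or 0.7 per month), the pre-operative weight is 0.18 or 0.21 and the estimate is 4.27 or 4.11.

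**3. Power for a 5.2-point post-operative benefit.** The variance of the difference is 64 × factor × 2/n. The literal model has effect 4.33 and factor (1 + 5ρ)/6. The baseline-adjusted five-visit average has effect 5.2 and factor (1 + 4ρ)/5 − ρ². At ρ = 0.28 and n = 21 the standard errors are √(64 × 0.400 × 2/21) = 1.56 and √(64 × 0.3456 × 2/21) = 1.45. The group-by-time test is an F test on 5 and 5(2n − 2) df.

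| Test | n per arm | ρ 0.28 | ρ 0.4 | ρ 0.5 |
|---|---|---|---|---|
| Literal, 6 scores | 21 | 77% | 68% | 61% |
| Literal, 6 scores | 30 | 90% | 83% | 77% |
| Group-by-time | 21 | 36% | 43% | 51% |
| Group-by-time | 30 | 51% | 60% | 70% |
| Baseline-adjusted, 5 visits | 21 | 94% | 93% | 93% |
| Baseline-adjusted, 5 visits | 30 | 98% or more | 98% or more | 98% or more |

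For 90% power the literal model needs 30 per arm at ρ = 0.28 and 43 at ρ = 0.5. The adjusted model needs 19 to 20 at either value.

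**4. The significance-triggered rule.** In 20,000 simulated trials at 21 per arm, applying the rule to baseline ODI raised literal-model power only from 77% to 79% (ρ = 0.28) and from 61% to 63% (ρ = 0.5). Type I error was 0.051 for the literal model, 0.040 and 0.034 with the rule, and 0.052 for the adjusted model.

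**5. Incomplete patients.** A patient with only a pre-operative score still enters the literal model and adds weight to the point that carries no effect. With 30 per arm, ρ = 0.28 and 0 / 3 / 5 / 9 such patients per arm, the estimate is 4.33 / 4.15 / 4.01 / 3.70 and power is 90 / 86 / 82 / 71%. The adjusted model keeps 93% or more. Nine per arm is the whole allowance from 30 to 21 and is a worst case, since II.D expects little drop-out.

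**The case against.** - **The sentence may name factors, not every model term.** II.E contrasts the mixed model with a two-way ANOVA, which ordinarily includes the interaction, and the pain sentence speaks of an effect over time. A group-by-time test would not dilute the effect. This stands as a possible intention, but the plan does not state it. For a constant benefit that test has only 36 to 51% power at 21 per arm (ρ 0.28 to 0.5). At ρ = 0.7 it reaches 77% and overtakes the literal model (51%), but not the adjusted average (98%).
- **Only the five post-operative scores may be meant as outcomes.** The estimate is then the full 5.2, with unadjusted power at 21 per arm of 88% (ρ = 0.28) or 76% (ρ = 0.5). The count of six in II.B points the other way, and adjustment still does better.
- **5.2 may be the average over all six points.** The literal model then keeps 90% power at 21 per arm and ρ = 0.28, but this implies a post-operative benefit of 5.2 × 6/5 = 6.24, which II.B does not state. Power is also 90% if correlation decays at 0.5 per month.
- **A late effect favours the interaction.** For 5.2 points at months 6 and 12 only (ρ = 0.28), group-by-time has 56% power at 21 per arm and 75% at 30. The adjusted five-visit average has 29% and 39%, and the literal model 19% and 26%. This is a real cost of a five-visit average and makes the choice of primary contrast debatable. It does not support leaving the contrast unnamed or the baseline unadjusted.
- **The harm is conservative.** Agreed: no false-positive inflation arises.

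**Conclusion.** The concern holds and should be fixed. As written, the primary model does not define its treatment test, and on its literal reading it reduces a constant 5.2-point post-operative benefit to about 4.33. Power at 21 per arm falls to about 77% at ρ = 0.28 and 61% at ρ = 0.5. At ρ = 0.28 the drop-out allowance is fully used to recover 90%.

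The 4.33 rests on additive terms, the pre-operative score as an outcome, equal correlation and complete data. Month-decaying correlation and baseline-only patients both make the dilution larger. The power figures also depend on an assumed ρ and on 5.2 being the post-operative difference. The missing prespecified baseline adjustment does not depend on any of these assumptions.

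**What to change.** **In II.E:**
- Use the five post-operative ODI scores as outcomes, with treatment, categorical visit, treatment-by-visit and pre-operative ODI as a prespecified covariate, whether or not the arms differ at baseline. Equivalently, keep all six scores in a constrained longitudinal model with a common baseline mean. With complete data the two give the same variance for the five-visit average (2.107 at ρ = 0.28, 21 per arm).
- Name one primary contrast. The treatment difference averaged over the five post-operative visits fits the on-average hypothesis in II.B. Report visit-specific differences, including month 12, as supportive.
- Use the same model for back and leg pain, each with its own baseline.

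**In II.B:** state the assumed within-patient correlation and its structure, say whether 5.2 is the post-operative difference or a six-point average, and restate power for the named test.

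**Cost:** wording only. The covariate is already collected, and no patients or visits are added. The drawback is that a late-only effect is still diluted: 5.2 points at months 6 and 12 average to 5.2 × 2/5 = 2.08 over five visits, against 5.2 × 2/6 = 1.73 over six. A single month-12 test avoids this but has only 57 to 66% power at 21 per arm and 73 to 82% at 30 (ρ 0.28 to 0.5). If the sponsor expects a late effect, the choice of contrast should be justified on that ground.
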